### 9.2.1.1. Cohort 1A: PK Visit 1a/1b

After study entry, PK Visit 1a and 1b for the neonate will be scheduled at **≥14 days and <28 days of life**. On the morning of the PK visit 1a, study nurses and physicians will take a medical history and examine the neonate. Afterwards, a single 5 mg dose of DTG (half of the 10 mg DTG-DT) will be administered. The study team will support the preparation and administration of the DTG-DT mixed with water with the parent(s) or caregiver/legal guardian and document the exact time of intake used for administration. Acceptability testing of the DTG-DT will be performed.

Following an observed dose, blood will be drawn at 1, 2, 3, 4, 6 (PK Visit 1a) and 24-30-hours (PK Visit 1b) post-dose. A blood draw window of +/- 15 minutes is acceptable for samples up to 6 hours post-dose. The last samples can be drawn anytime between 24 and 30-hours post-dose. It is planned to draw 0.4 mL per time point - a total blood volume of 2.4 mL for PK assessment. A short intravenous catheter (heparin lock) can be used to reduce repeated skin puncture and ease the discomfort of blood sampling.

### 9.2.1.2. Cohort 1A: Safety Visits

One week after PK visit 1a (+/-4 days), we will conduct a clinical and laboratory safety visit. Medical staff will take a recent medical history from the parent(s) or caregiver/legal guardian and examine the neonate. Study required bloods will be drawn, and an HIV NAT will be performed. If any tests yield abnormal results, as specified by protocol specific safety criteria (Section 10), we will consult paediatricians for appropriate management of the neonate. If the clinical examination and all tests are normal, a telephonic safety visit will be conducted 2 weeks after PK Visit 1a (+/-4 days). Medical staff will once again take a recent medical history from the parent(s). If no issues are reported, the neonate will exit the study at the conclusion of this visit. If any concerns are noted, the neonate will be brought back for clinical and special investigations as needed. The total study duration for each individual will depend on the age at enrolment and can range from 2 to 6 weeks.

If study safety hold criteria (Section 11.1.1) are met at any time during Cohort 1A the study will be paused, safety data reviewed, and a DSMB meeting held to determine if the study should continue (Section 6.2, **Figure 1**). After Cohort 1A is complete, if no major safety concerns are noted, accrual will continue into Cohort 1B.

### 9.2.2. Stage 1: Cohort 1B

The screening and entry visit(s) will take place within ≤3 days of life. Screening and entry procedures may be performed as one or 2 separate visit(s). HIV-exposed neonates enrolled in Cohort 1B will continue to receive ARV prophylaxis as per local guidelines for the duration of the study.

If an HIV NAT test result comes back positive for a neonate at any time during the study, the neonate will not receive any further study drugs, come off study and will be treated as per standard of care (any prior PK samples will be included in the analysis).

At the end of study follow-up, HIV negative infants will continue standard of care HIV prophylaxis, if indicated, as per local guidelines.

### 9.2.2.1. Cohort 1B: PK Visit 1

After study entry, PK visit 1a and 1b for the neonate will be scheduled at **< 14 days of life**. On the morning of the PK visit, study nurses and physicians will take a medical history and examine the neonate. Afterwards, a single 5 mg dose of DTG (half of the 10 mg DTG-DT) will be administered. The study team will support the preparation and administration of the DTG-DT mixed with water with the mother and document the exact time of intake used for administration. Acceptability testing of the DTG-DT will be performed.

Blood will be drawn pre-dose, and then following an observed dose, at 1, 2, 4, and 6 (PK Visit 1a), and 24-72 hours (PK Visit 1b) post-dose. A blood draw window of +/- 15 minutes is acceptable for samples up to 6 hours post-dose. The last sample can be drawn anytime between 24 and 72-hours post-dose. It is planned to draw 0.4 mL per time point - a total blood volume of 2.4 mL for PK assessment. A short intravenous catheter (heparin lock) can be used to reduce repeated skin puncture and ease the discomfort of blood sampling.

### 9.2.2.2. Cohort 1B: Safety Visits

One week after PK Visit 1a (+/-4 days), we will conduct a clinical and laboratory safety visit. Medical staff will take a recent medical history from the parent(s) and examine the neonate. Study required bloods will be drawn, and an HIV NAT will be performed. If any tests yield abnormal results, as specified by protocol specific safety criteria (Section 10), we will consult with paediatricians for appropriate management of the neonate. If all tests are normal, a telephonic safety visit will be conducted 2 weeks after PK Visit 1a (+/-4 days). Medical staff will once again take a recent medical history from the parent(s). If no issues are reported, the neonate will exit the study at the conclusion of this visit. If any concerns are noted, the neonate will be brought back for clinical and special investigations as needed. The total study duration for each individual will depend on the age at enrolment and can range from 3 to 4 weeks.

If study safety hold criteria (Section 11.1.2) are met at any time during Cohort 1B the study will be paused, safety data reviewed, and a DSMB meeting held to determine if the study should continue (Section 6.2, **Figure 1**). After Cohort 1B is complete, all safety and PK data for Stage 1 will be reviewed. Pharmacokinetic modelling and simulation analyses using Stage 1 PK data will be performed to select the multi-dose schedule of 5 mg DTG for Cohort 2. All findings will be presented to the DSMB before opening Cohort 2 (Section 11.4).

### 9.2.3. Stage 2: Cohort 2

Low-risk HIV-exposed neonates in Cohort 2 will receive multiple 5 mg doses of DTG.

DTG administration will begin within 7 days of life and continue until day 28 of life on top of ARV postnatal prophylaxis. Due to the potential drug-drug interaction between NVP and DTG, the low-risk neonates enrolled in Stage 2 will receive ZDV prophylaxis, instead of NVP, for the duration of the study (Section 8.2.1 and Section 13.6).

Due to the fixed 5 mg DTG dose, and the anticipated slow metabolism in neonates, the multiple DTG dosing schedule will likely require longer dosing intervals during early life compared to older infants (e.g., every 48 or 72 hours compared to every 24 hours (Section 8.2.1). Possible DTG dosing schedules for 5 mg of the dispersible tablet during the first 28 days of life are shown in **Table 4**. The pharmacokinetic modelling and simulation analyses of Stage 1 PK data will support the multi-dose schedule of 5 mg DTG for Cohort 2.

**Table 4:** Potential multi-dose schedules of 5 mg DTG for neonates in Cohort 2 during the first 4 weeks of life.

DTG 5 mg Dosing Schedule	Neonate - Week of Life			
	1	2	3	4
1	Q72 hrs		Q48 hrs	
2	Q72 hrs		Q24 hrs	
3	Q48 hrs		Q48 hrs	
4	Q48 hrs		Q24 hrs	
5	Q24 hrs		Q24 hrs	

*Note: \*A DTG dosing schedule not listed in the table may be selected based on the PK analysis from Stage 1, and may differ by birth weight (e.g., above and below 3000 g)*

If an HIV NAT test result comes back positive for a neonate at any time during the study, the neonate will not receive any further study drugs, come off study and will be treated as per standard of care (any prior PK samples will be included in the analysis).

At the end of study follow-up, HIV negative infants will continue standard of care HIV prophylaxis, if indicated, as per local guidelines.

An interim PK and safety analysis will be performed after 50% of participants have completed Cohort 2 to assess if a dose adjustment is required and to review safety data. Following the DSMB interim review, a different DTG dosing schedule may be selected based on the data available for the remainder of Cohort 2 infants. Any change to the DTG dosing schedule will be agreed upon by the DSMB before implementation.

### 9.2.3.1. Cohort 2: Screening and Entry visit(s)

The screening and entry visit(s) will take place when the neonate is <7 days of life (Section 9.1). Screening and entry procedures may be performed as one or 2 separate visit(s). At the Entry visit, ZDV prophylaxis will be initiated instead of NVP and continue until DTG is stopped at Day 28 of life. Thereafter, the infant will switch back to NVP from ZDV and continue prophylaxis per national guidelines.

The study team will support the preparation and administration of the 1st dose of the DTG-DT (half-tablet) mixed with water with the parent(s) or caregiver/legal guardian. The exact time of intake will be recorded. The mother will be explained how to prepare and administer DTG at home. Acceptability testing of the DTG-DT will be performed.

Two blood samples will be drawn for PK assessment, one sample immediately prior to administering the 1st DTG dose and another sample at 1-3 hrs post-dose (**Table 5**). It is planned to draw 0.4 mL of blood per time point.

### 9.2.3.2. Cohort 2: Study Visits 2 and Visit 3

It is anticipated that DTG could be dosed every 24, every 48 or every 72 hours, or some other combination, that is expected to achieve target DTG concentrations throughout the first 4 weeks of life. The PK sampling schedule has been designed to cover these different possible dosing scenarios.

After the Entry, Visit 2 can be scheduled at **any time from the 3rd dose of DTG** but before Week 4 of life. The mother will be instructed not to administer the morning DTG dose prior to attending this study visit. On the morning of Visit 2, clinic study nurses and physicians will take a medical history, examine the neonate, and assess adherence. Assessments will include dispensing diary cards to caregivers, reviewing or collecting diary cards and establishing study drug adherence (pill count). The PK assessment should be deferred if the mother/caregiver reports their baby missing any of the previous 3 scheduled doses prior to the PK sampling visit (Section 9.4).

Prior to the morning DTG dose, a blood sample will be taken for pre-dose PK evaluation and then the protocol-specified DTG dose will be administered. The exact time of intake will be recorded. Acceptability testing of the DTG-DT will be performed.

Following an observed dose, blood will be drawn pre-dose, and at 1, 2, 4, and 6 (Visit 2), and 24-72 hours (Visit 3) post-dose (**Table 5**). A blood draw window of +/- 15 minutes is acceptable for samples up to 6 hours post-dose. The last sample can be drawn anytime between 24 and 72-hours post-dose. It is planned to draw 0.4 mL per time point - a total blood volume of 2.4 mL for PK assessment. A short intravenous catheter (heparin lock) can be used to reduce repeated skin puncture and ease the discomfort of blood sampling.

#### 9.2.3.3. Cohort 2: Visit 4

At least 1 week after Visit 2 (+/-4 days), we will conduct a clinical and laboratory safety visit. Medical staff will take a recent medical history from the parent(s) and examine the neonate. Study required bloods will be drawn. If any tests yield abnormal results, as specified by protocol specific safety criteria (Section 10), we will consult with paediatricians for appropriate management of the neonate. Adherence assessments will include dispensing diary cards to caregivers, reviewing or collecting diary cards and establishing study drug adherence (pill count). Acceptability testing of the DTG-DT will also be performed. Note: Visit 4 can be conducted on the same day as Visit 5, but only if both fall within week 4 of life.

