Physical examination b	X	X		X	
Dispense Study Drug		X			
Acceptability questionnaire		X			
Laboratory					
Haematology c	X (0.5 mL)			X (0.5 mL)	
Chemistry d	X (0.8 mL)			X (0.8 mL)	
HIV-1 NAT Test e	X (0.8 mL)			X (0.8 mL)	
Pharmacology					
PK Blood Sampling f		X (2 mL)	X (0.4 mL)		
Total blood volume	2.1 mL	2 mL	0.4 mL	2.1 mL	

a Screening and entry procedures may be performed as one or 2 separate visit(s). All study required results should be available before entry with the exception of the HIV-1 NAT result which may be pending at time of study entry; b Physical and medical assessment includes length, weight, head measurements and monitoring of vital signs; c Haemoglobin, white blood cell count and differential, and platelets; d Creatinine, ALT, AST, total and direct bilirubin; e If HIV-1 NAT Test comes back positive, the HIV-infected neonate will be taken off study and initiated on standard of care HIV-treatment, as per local guidelines; f PK blood sampling will occur at the following time points: pre-dose and 1, 2, 4, 6 and 24-72 hours post dose. Mothers and their neonates will return home after PK Visit 1a and attend 24–72 hours later (as applicable) for PK Visit 1b. Laboratory tests may be repeated during the screening period dependent on specified blood draw limits.

**Table 8.** Schedule of evaluations for Stage 2 Cohort 2 (n=24): Multiple doses of DTG in neonates commencing within 72 hours of life

Evaluation	Screening and Entry Visit(s) a	Visit 2	Visit 3	Visit 4	Visit 5	Safety Phone Call
Visit windows	< 7 days of life	Any time from 3 rd DTG dose but before Week 4 of life b	24 to 72 hours post Visit 2 DTG dose	1 week after Visit 2 (+/- 4 days) c	Week 4 of life (Day 22 – 28 of life)	2 weeks after Visit 5 (+/-4 days)
Clinical						
Informed Consent	X					
History	X	X	X	X	X	X
Physical examination d	X	X		X	X	
Dispense Study Drug e	X	X	X	X	X	
Acceptability questionnaire	X	X		X	X	
Adherence assessments		X		X	X	
Laboratory						
Haematology f	X (0.5 mL)			X (0.5 mL)		
Chemistry g	X (0.8 mL)	X (0.8 mL)		X (0.8 mL)	X (0.8mL)	
HIV-1 NAT Test f	X (0.8 mL)				X (0.8 mL)	
Pharmacology						
PK Sampling i	X (0.8 mL)	X (2.0 mL)	X (0.4 mL)		X (0.8mL)	

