Total blood volume	2.9 mL	2.8 mL	0.4 mL	1.3 mL	2.4 mL	

a Screening and entry procedures may be performed as one or 2 separate visit(s). All study required results should be available before entry with the exception of the HIV-1 NAT result which may be pending at time of study entry; b Visit 2 and 3 should be scheduled any time from 3rd DTG dose but before week 4 of life; c Visit 4 can be conducted on the same day as Visit 5 but only if both falls within week 4 of life; d Physical and medical assessment includes length, weight, head measurements and monitoring of vital signs vital signs; e 1st DTG dose administered <7 days. The timing of the next dose of DTG and subsequent DTG doses will be determined using data from Cohort 1A and 1B. DTG will be administered until the neonate is 28 days old; f Haemoglobin, white blood cell count and differential, and platelets; g Creatinine, ALT, AST, total and direct bilirubin; h If HIV-1 NAT Test comes back positive, the HIV-infected neonate will be taken off study and initiated on standard of care HIV-treatment, as per local guidelines; i For the 1st DTG dose (PK: pre-dose sample and 1 more sample 1-3 hours post-dose); Any time from 3rd DTG dose but before week 4 of life (PK: pre-dose and 1, 2, 4, 6 and 24-72 hours post dose); For any DTG dose in Week 4 of life (PK: pre-dose sample and another sample 1-3 hours post-dose). Laboratory tests **may not** be repeated during the screening period as this will exceed blood draw limits.

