## 10.7. Risk of Elevated Bilirubin Levels in neonates

### 10.7.1. Bilirubin Metabolism in Neonates

Between 25-50% of all term neonates develop clinical jaundice characterized by high levels of unconjugated/free bilirubin. The serum bilirubin of term neonates rises to a peak of 103 to 137  $\mu\text{mol/L}$  by 3 days of life and then falls. A rise to 205  $\mu\text{mol/L}$  is still within the normal physiological range and may be attributed to an increase in bilirubin production, reduced uptake of bilirubin from plasma, reduced conjugation (immature UGT1A1 enzyme activity) and decreased hepatic excretion of bilirubin (46). Bilirubin values exceeding 342  $\mu\text{mol/L}$  have been considered levels at which kernicterus can occur (48, 49). Phototherapy are the mainstay of treatment for unconjugated hyperbilirubinemia resulting in less free bilirubin available to cross the blood-brain barrier, and thereby protecting against kernicterus and associated brain damage. In rare cases, exchange transfusions are performed to rapidly decrease bilirubin values.

Normally, newborn produce more bilirubin compared to adults. After birth, fetal haemoglobin is broken down and replaced with adult haemoglobin. Heme-containing proteins from old red cells are converted to insoluble bilirubin which is then bound to albumin and transported to the liver. Once in the liver, the enzyme UGT1A1 converts the unconjugated bilirubin to water-soluble conjugated bilirubin. End-products of this process, i.e., bile, is then secreted into the digested tract with bilirubin metabolites leaving the body through faeces (50).

The bilirubin-conjugating capacity of infants is dependent on UGT1A1 enzyme activity, which is typically slow at birth but rapidly increases in the first months of life. UGT1A1 is expressed at 1% of adult levels between 30- and 40-weeks' gestation, reaching adult levels by 14 weeks of postnatal life (51). Immature UGT1A1 early in life may lead to less conjugation and contribute to elevated free bilirubin levels leading to the jaundice in the newborn.

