### 10.7.2. Dolutegravir, Protein Binding and Hyperbilirubinemia

Dolutegravir is a well-tolerated potent ARV with minimal side effects. The drug is highly bound to plasma proteins and can displace bilirubin from albumin. DTG poses a theoretical risk of increased free bilirubin concentrations in the neonate at high DTG concentrations and in the presence of low serum albumin. However, DTG concentrations achieved in adults at approved DTG dosing are much lower than concentrations expected to result in the displacement of bilirubin from albumin (52).

An *in-vitro* experiment performed in the presence of low albumin concentrations has shown DTG to displace bilirubin from albumin to an equivalent extent as sulfisoxazole, raising concerns of increased free bilirubin and risk of bilirubin neurotoxicity. The clinical relevance of these experimental findings are however unclear as normal albumin concentrations (500-700 µmol/L) in adults and children typically exceeds DTG plasma concentrations by around 100-fold. The authors conducting these *in-vitro* studies conclude that unless the DTG concentrations are very high in a neonate, it is unlikely to have a significant impact on bilirubin to albumin binding because of the low DTG concentrations relative to the amount of albumin in the body (52).

To minimize the risk of bilirubin toxicity, we will exclude neonates born from mothers with known blood group incompatibility that can result in haemolytic disease of the newborn. We will not enroll neonates at high risk of bilirubin toxicity, which include preterm neonates, unwell neonates with a history of birth trauma, those with hypothermia, or suspected sepsis (53). Neonates with very high bilirubin values close to exchange, as defined by local guidelines (47), will also not be eligible for the study. Total and direct bilirubin will be drawn at baseline and monitored throughout the study. For safety purposes, a single dose of DTG will first be administered to older neonates (>2 weeks of age) in Cohort 1A, before moving to a single dose in younger neonates (<2 weeks of age) in Cohort 1B. Only if no safety concerns are observed will a multi-dose DTG strategy be considered, and neonates enrolled into Cohort 2.

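### In Cohort 2 no safety blood between Entry and Week 4 is fixed to age or time on drug, so permitted booking can leave 15 to 20 days of dosing before the first on-treatment chemistry

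*Protocol*

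**What the plan says.** Section 9.2.3 of the protocol sets the Cohort 2 dosing period: "DTG administration will begin within 7 days of life and continue until day 28 of life". Table 8 (Section 9.3) schedules chemistry at Entry and at Visits 2, 4 and 5. It schedules haematology at Entry and Visit 4 only. The visits are placed as follows.

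- **Visit 2** (Section 9.2.3.2) is the intensive PK day. It is allowed from the third dose "but before Week 4 of life", and footnote b of Table 8 repeats the limit: "DTG dose but before week 4 of life". Section 9.4 defers it if any of the last three doses was missed.
- **Visit 4** is timed only from Visit 2. Section 9.2.3.3 says "At least 1 week after Visit 2 (+/-4 days), we will conduct a clinical and laboratory safety visit". Table 8 says "1 week after Visit 2 (+/- 4 days". It may share a day with Visit 5 if both fall in week 4.
- **Visit 5** (Section 9.2.3.4) is fixed by age, at day 22 to 28. Dosing stops by day 28.

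Between Entry and Visit 2, Section 8.4 plans only a contact with the mother to check that doses were given. Section 10.7.2 states the intent for bilirubin: "Total and direct bilirubin will be drawn at baseline and monitored throughout the study".

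In Cohorts 1A and 1B (Sections 9.2.1.2 and 9.2.2.2), safety bloods are drawn one week, plus or minus 4 days, after the day of the single dose.

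**The concern.** Adverse events of Grade 3 or higher are a primary endpoint (Section 5.3.1), and under Section 10.1 new or worsening laboratory abnormalities count as adverse events. A laboratory event can be counted only if blood is drawn while it is present. In Cohort 2 the early draws follow the booking of the PK day, so the part of treatment that is observed differs from infant to infant.

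The protocol itself describes early life as the period of slow metabolism. Section 10.7.1 says of bilirubin "The serum bilirubin of term neonates rises to a peak of 103 to 137" µmol/L by day 3 and describes UGT1A1 as immature. Section 8.2.1 expects slower dolutegravir elimination. The hold rule in Section 11.1.3 (3 of the first 12, or 6 of 24, with the same related event of Grade 3 or higher) and the review at 50% of Cohort 2 both depend on what these draws detect.

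**Working it through.** **Inputs and conventions.** Birth is day 1. The first dose is on day 1 to 6 (under 7 days of life). Doses are every 24, 48 or 72 hours (Table 4). Visit 2 runs from the third dose to day 21, since Week 4 is day 22 to 28. Visit 4 is Visit 2 + 7 ± 4 days, that is +3 to +11, as Table 8 reads; it is +7 to +11 if the words requiring at least a week in Section 9.2.3.3 are taken strictly. Visit 5 is day 22 to 28. A different day-numbering convention would shift results by about a day.

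**Step 1, the plan's own volumes.** Table 8 reproduces: Entry 0.5 + 0.8 + 0.8 + 0.8 = 2.9; Visit 2 0.8 + 2.0 = 2.8; Visit 3 0.4; Visit 4 0.5 + 0.8 = 1.3; Visit 5 0.8 + 0.8 + 0.8 = 2.4. The total is 9.8 mL, against a 30-day limit of 10 mL at 2 kg (Section 13.7).

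**Step 2, first dose to first on-treatment chemistry.** The longest gap is 21 minus the day of first dose:

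| First dose | Latest Visit 2 | Gap |
|---|---|---|
| Day 1 | Day 21 | 20 days |
| Day 3 | Day 21 | 18 days |
| Day 6 | Day 21 | 15 days |

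For a day-1 start, days 1 to 20 hold 20, 10 or 7 doses at 24, 48 or 72 hour intervals.

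**Step 3, early Visit 2.** Early booking does not bound the gap. With a first dose on day 1 at 24 hours, Visit 2 can be on day 3. Under Table 8, Visit 4 can then be on day 3 + 3 = 6 and Visit 5 on day 28, a gap of 28 − 6 = 22 days. Under the strict reading Visit 4 is no earlier than day 3 + 7 = 10, and the later gap is at most 28 − 10 = 18 days.

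**Step 4, Visit 4 after dosing.** Visit 4 passes day 28 when Visit 2 + 11 > 28, so a Visit 2 on day 18 to 21 permits it. The latest date is 21 + 11 = day 32. At the nominal +7 days it never passes day 28 (21 + 7 = 28).

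**Step 5, the protocol's own comparison.** In Cohorts 1A and 1B the latest safety blood is 7 + 4 = 11 days after a single dose. Repeatedly dosed infants can wait up to 20.

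**Step 6, room for a fix.** One added chemistry draw gives 9.8 + 0.8 = 10.6 mL, over 10 mL at 2 kg (though under 12 mL at 3 kg). For the smallest infants, existing draws must be moved rather than one added. The third dose comes 2, 4 or 6 days after the first at 24, 48 or 72 hours, so Visit 2 can itself fall within 11 days of the first dose on all three intervals.

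**The case against.** The wide Visit 2 window has a stated purpose: Section 9.2.3.2 explains that the sampling had to cover dosing schedules not yet known. The figures above are permitted extremes, not expected practice; 20 doses before chemistry needs a day-1 start, daily dosing and Visit 2 on its last day, while Section 9.2.3 expects longer intervals in early life. Standard-of-care bilirubin checks remain possible, and parent-reported events are captured. All of this stands and limits the severity. It does not remove the gap, because nothing in the document caps it.

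A reader might infer several stronger points that the documents do not support.

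- **That all on-treatment safety bloods depend on Visit 2.** Visit 5 chemistry is fixed at day 22 to 28.
- **That weeks 1 to 3 contain no examination or blood.** Entry has both, and so does a Visit 2 on day 21.
- **That three draws can crowd into one week with one of them after dosing.** Each is permitted, but not together if dosing runs to day 28: Visit 2 on day 21 and Visit 4 on day 29 already span 8 days.
- **That severe bilirubin events would go unrecorded.** Table 9 grades bilirubin by intervention or clinical state (exchange transfusion is Grade 3, encephalopathy Grade 4), and these are not silent laboratory values.
- **That the day-3 bilirubin peak is necessarily missed on drug.** An infant may first be dosed after it.
- **That Section 10.7.2 is flatly contradicted.** It promises no frequency; the windows merely fail to guarantee monitoring throughout.

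**Conclusion.** The point holds as a should-fix weakness in the timing of safety assessments. Before Week 4 nothing ties a post-baseline safety blood to age or time on drug. The permitted worst cases are 15 to 20 days of dosing before the first on-treatment chemistry, 22 days between later draws after an early Visit 2 (Table 8 window), and the only post-baseline haematology on day 29 to 32. The consequence is under-ascertainment of ALT, AST and creatinine rises that resolve between draws; such rises would reach neither the primary safety endpoint nor the hold rule. The documents give no basis for estimating how many events this would be.

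The conclusion rests on the day-numbering above and concerns scheduled tests only. Separately, the Visit 4 wording is ambiguous, since a minimum of one week does not sit with a tolerance of minus 4 days. The start of dosing also needs reconciling: Section 9.2.3 allows the first 7 days, while the title of Table 8 reads "Multiple doses of DTG in neonates commencing within 72 hours of life".

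**What to change.** Amend Section 9.2.3.3 and Table 8 as follows.

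1. Set an upper limit from first dose to first on-treatment chemistry, for example by using the Cohort 1 window of one week ± 4 days. Visit 2 meets it if held early enough; otherwise Visit 4 is held before Visit 2. If Visit 2 is deferred under Section 9.4, the limit still triggers Visit 4. The longest first gap falls from 20 to 11 days.
2. Require Visit 4 on or before Visit 5, so that no draw meant as on-treatment falls after dosing ends.
3. Where Visit 4 is held early, move its 0.5 mL haematology to Visit 5. Visit 4 becomes 0.8 mL and Visit 5 becomes 2.9 mL. The total is 2.9 + 2.8 + 0.4 + 0.8 + 2.9 = 9.8 mL, unchanged and within 10 mL at 2 kg. Without this step, bringing Visit 4 forward would leave the later weeks with no haematology.
4. State one Visit 4 window in both places. This choice also settles the gap after an early Visit 2, which item 1 does not shorten: 22 days as Table 8 reads, 18 under the strict reading. A stated maximum interval between chemistry draws would be needed to go lower.

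The cost is a protocol amendment, less freedom in booking, and no early haematology for infants whose Visit 4 is brought forward. The number of visits does not change.
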